8.4.2 Body measurements

Height (cm), at screening

Body Weight (kg), with 1 decimal.

The body weight assessed at each visit will be used for determination of the concizumab dose to be administered until next visit.

Measurements will be reported in the eCRF

Protocol
 Trial ID:NN7415-4255
 UTN:U1111-1179-3872
 EudraCT no.:2016-000614-29

~~CONFIDENTIAL~~

Date: 28 August 2018
 Version: 5.0
 Status: Final
 Page: 61 of 127

Novo Nordisk

8.4.3 Vital signs

Before measurement of vital signs the patient should preferably rest comfortably for at least five minutes and all measurements should, if possible, be performed using the same method and sitting position throughout the trial.

Measurements at visits must be performed prior to any trial product administration unless otherwise specified

- Body temperature (°C)
- Systolic and diastolic blood pressure, sitting (BP) (mmHg)
- Pulse, sitting (beats/min)
- Respiratory rate

Exception: At visit 2, the measurement is also performed after concizumab administration.

The investigator must evaluate the results and classify the outcome as either:

- Normal or abnormal
- If abnormal the investigator must:
 - Specify the abnormality
 - Record if the result is clinically significant (Yes/No)
 - If observed before or at screening: record as concomitant illness (section [8.2.2.](#))
 - If observed after screening: report an AE/SAE (section [12](#))

Measurements will be reported in the eCRF.

8.4.4 Electrocardiogram

The investigator must evaluate the ECG (standard 12 lead) at screening and classify the outcome as either:

- Normal or Abnormal.
- If Abnormal the investigator must:
 - Specify the abnormality
 - Record if the result is clinically significant? (Yes/No)
 - If observed before or at Screening: record as Medical History (Section [8.2.1](#))
 - If observed after screening: report an AE/SAE (Section [12](#))

The ECG results must be dated and signed by the investigator to verify that the data have been reviewed. Outcome will be reported in the eCRF.

8.4.5 Adverse events

Adverse events (AEs) must be reported at each visit in accordance with the procedures outlined in Section [12](#).

Protocol
Trial ID:NN7415-4255
UTN:U1111-1179-3872
EudraCT no.:2016-000614-29

~~CONFIDENTIAL~~

Date: 28 August 2018
Version: 5.0
Status: Final
Page: 62 of 127

Novo Nordisk

8.4.5.1 Medication error

If a medication error is observed during the trial, the following information is required and a specific event form must be completed in the eCRF in addition to the AE form:

- Trial product(s) involved
- Classification of medication error
- Whether the patient experienced any adverse event(s) as a result of the medication error
- Suspected primary reason for the medication error

For definition of medication errors, see Section [12.1.4](#).

8.4.5.2 Adverse events requiring additional data collection

For the following AEs additional data collection is required and specific event forms must be completed in the eCRF in addition to the AE form

In case any of these events fulfil the criteria for a serious adverse event, please report accordingly, see Section [12](#).

Injection site reaction

Investigation of injection site reactions will be performed locally at visit 2 based on patient feedback and by following visual inspections of injection sites for concizumab administration:

Symptoms e.g.

- Pain
- Numbness
- Itching
- Burning

Signs e.g.:

- Redness (mm x mm)
- Induration (mm x mm)
- Swelling
- Dimpling
- Macula
- Haematoma
- Bleeding
- Other (visual reactions)

Any injection site reaction symptom (evaluated between visit 2-16) should be recorded in the AE form and the injection site reaction form, see section [12.1.5](#).

Protocol
 Trial ID:NN7415-4255
 UTN:U1111-1179-3872
 EudraCT no.:2016-000614-29

~~CONFIDENTIAL~~

Date: 28 August 2018
 Version: 5.0
 Status: Final
 Page: 63 of 127

Novo Nordisk

A separate AE should be recorded for each injection site reaction symptom. The affected area should also be evaluated for redness and induration in mm using a ruler. To ensure all local injection site assessments are performed at the injection site, the area around the site will be marked with a pen prior to injection.

In the event of a local reaction, additional visual assessments (as described above) will be performed until resolution as judged necessary by the investigator.

Assessment of injection site reactions can be performed at any time, if deemed necessary by the investigator.

Hypersensitivity reaction

If suspicion of a hypersensitivity reaction occurs the patients should be instructed to contact the site staff as soon as possible for further guidance.

All events of hypersensitivity reactions must be reported and the following information must be obtained if available on the hypersensitivity reaction form:

- Signs and symptoms associated with the event
- Time of appearance after administration of trial drug
- Relevant immunological tests performed (See section [8.5.2.7](#))
- Treatment given for the reaction
- Previous history of similar reactions
- Association with the trial product(s)
- Relevant risk factors associated with the event
- Storage condition of the trial product
- Total number of doses, from first day on trial product, up to the time of this event

8.5 Laboratory assessments

An approximate total blood volume of 686 mL will be taken from each patient in the trial. Ports cannot be used for blood sampling.

A laboratory manual will be provided for detailed description of obtaining and processing blood samples.

All laboratory blood samples collected for this trial except for haematology samples are to be shipped for analysis at central laboratories or further distribution to special laboratories.

Haematology samples are to be analysed locally.

The laboratory provides results to the trial sites in the units preferred by the trial sites while the results that are transferred to the trial database will always be in international system of units (SI).

Protocol
 Trial ID:NN7415-4255
 UTN:U1111-1179-3872
 EudraCT no.:2016-000614-29

~~CONFIDENTIAL~~

Date: 28 August 2018
 Version: 5.0
 Status: Final
 Page: 64 of 127

Novo Nordisk

Laboratory reports listing results from centrally analysed samples will be made available for the investigator. Investigator must review and evaluate the results and report AEs for results which are clinical significant. Laboratory reports will where possible indicate normal ranges

Categorisation of clinical significance for out of range results may not be required for the following laboratory parameters and the investigator is therefore not required to perform a categorisation even though these parameters are listed in the laboratory report: FVIII activity, FVIII inhibitor test, Thrombin generation, TFPI not bound to concizumab, concizumab concentration in plasma, Anti-concizumab binding antibodies, and Total TFPI.

The laboratory equipment may provide analyses not requested in the protocol but produced automatically in connection with the requested analyses according to specifications in the laboratory standard operating procedures. Such data will not be transferred to the trial database, but abnormal values will be reported to the investigator. The investigator must review all laboratory results for concomitant illnesses and AEs and report these according to section [8.2.2](#) and section [12](#).

Only laboratory samples specified in the protocol must be sent to the central laboratory for analysis; if additional laboratory sampling is needed, e.g. to follow up on AEs, this must be done at a local laboratory except for biomarkers and anti-drug antibodies (anti-concizumab IgE antibodies and anti-concizumab binding antibodies).

Laboratory samples will be destroyed no later than at finalisation of the clinical trial report (CTR).

Antibody samples and human bio-samples, if applicable will be stored as described in section [24.2](#). The investigator may not be able to review the results of antibody measurements in relation to AEs as these are often analysed after LPLV.

8.5.1 Laboratory assessments for efficacy

8.5.1.1 Thrombin generation

The Thrombin Generation Assay (TGA) will be performed at all visits (including unscheduled 24 hour PK visit), except visit 3.

The TGA is included as an exploratory PD assessment.

The generation of thrombin is a fundamental part of the haemostatic system, and is a key measurable parameter of the formation of a clot under bleeding or thrombotic conditions. The thrombin burst is crucial for the formation of a stable fibrin clot.

The Calibrated Automated Thrombogram (CAT) method (used by Thrombinoscope BV) will be used to measure thrombin generation (TG). This method uses a slow acting fluorogenic substrate that allows continuous measurement of thrombin generation in double centrifuged citrated plasma.

Protocol
 Trial ID:NN7415-4255
 UTN:U1111-1179-3872
 EudraCT no.:2016-000614-29

~~CONFIDENTIAL~~

Date:	28 August 2018	Novo Nordisk
Version:	5.0	
Status:	Final	
Page:	65 of 127	

In this assay set-up thrombin generation is initiated by low-dose tissue factor that is combined with phospholipid. The result is obtained by comparison to a constant known thrombin activity in a parallel non tissue factor initiated sample. The assay has been validated fit-for-purpose.

The thrombin generation endpoints are defined, but not limited to,

- The Endogenous Thrombin Potential (ETP) – the area under the curve
- Peak thrombin generation
- Velocity Index

8.5.1.2 Free TFPI

Free TFPI measures TFPI not bound to concizumab. This enzyme-linked immunosorbent assay (ELISA) test will be sampled for at all assessment visits, including unscheduled 24 hour PK visit.

The free TFPI ELISA assay is an enzyme immunoassay measuring levels of TFPI not bound to concizumab from Diagnostica Stago (named and referred to Asserachrom TOTAL TFPI) and will be used for PD assessments.

Free TFPI is included as a PD assessment.

8.5.2 Laboratory assessments for safety

8.5.2.1 Urinalysis

- pH
- Protein
- Glucose
- Bilirubin

This is a semi qualitative measurement which will be performed (locally) at the screening visit by the site by using the appropriate reagent strips for urinalysis. The results will be recorded in the eCRF.

Clinically significant findings must be recorded as:

- Normal or abnormal
 - if abnormal the investigator must:
 - record if the result is clinically significant? (Yes/No)
 - If observed before or at screening: record as concomitant illness (section [8.2.2](#))

8.5.2.2 Haematology

Haematology samples are to be sampled and analysed locally at all visits, except visit 3.

Protocol
 Trial ID: NN7415-4255
 UTN: U1111-1179-3872
 EudraCT no.: 2016-000614-29

~~CONFIDENTIAL~~

Date:
 Version:
 Status:
 Page:

28 August 2018
 5.0
 Final
 66 of 127

Novo Nordisk

- Haemoglobin
- Erythrocytes (cell count)
- Thrombocytes (Platelet count)
- Leucocytes (cell count)
- Differential leucocytes cell count
 - Lymphocytes
 - Monocytes
 - Neutrophils
 - Eosinophils
 - Basophils

The investigator must evaluate the results and record the outcome as:

- Normal or abnormal
- If abnormal the investigator must:
 - Specify the abnormality
 - Record if the result is clinically significant (Yes/No)
 - If observed before or at screening: record as concomitant illness (section [8.2.2](#))
 - If observed after screening: report an AE/SAE (section [12](#))

Haematology results are to be entered into the eCRF.

8.5.2.3 Biochemistry

- Creatinine
- Albumin
- Bilirubin; total, direct and indirect)
- Aspartate aminotransferase (AST)
- Alanine aminotransferase (ALT)
- Gamma glutamyltransferase (GGT)
- Alkaline phosphatase
- C-reactive protein (CRP)

The investigator must evaluate the results and record the outcome as:

- Normal or abnormal
- If abnormal the investigator must:
 - Specify the abnormality
 - Record if the result is clinically significant (Yes/No)
 - If observed before or at screening: record as concomitant illness (section [8.2.2](#))
 - If observed after screening: report an AE/SAE (section [12](#))

Protocol
 Trial ID:NN7415-4255
 UTN:U1111-1179-3872
 EudraCT no.:2016-000614-29

~~CONFIDENTIAL~~

Date: 28 August 2018
 Version: 5.0
 Status: Final
 Page: 67 of 127

Novo Nordisk

8.5.2.4 FVIII activity

- FVIII activity (IU/ml)

8.5.2.5 Coagulation parameters

- Fibrinogen
- Prothrombin time (PT) including INR
- D-dimer
- Prothrombin fragment 1+2
- Activated partial thromboplastin time (APTT)
- Antithrombin (AT)

The investigator must evaluate the results and record the outcome as:

- Normal or abnormal
- If abnormal the investigator must:
 - Specify the abnormality
 - Record if the result is clinically significant (Yes/No)
 - If observed before or at screening: record as concomitant illness (section [8.2.2](#))
 - If observed after screening: report an AE/SAE (section [12](#))

8.5.2.6 FVIII inhibitor test

The inhibitor level of the patient will be measured by the Nijmegen method at visit 1 (screening).

- FVIII inhibitor titre (BU)

In order to minimise the risk of false negative results, circulating FVIII product levels should be less than 0.05 IU/ml, when sampling for the test. If the patient has received FVIII within 96 hours of screening, the sampling of FVIII-Inhibitor should be postponed until a time period equal to 8 half-lives of the used product has passed (counting from latest treatment).

8.5.2.7 Anti-concizumab antibodies

Sampling will be performed at all visits except at visit 3. Samples will be collected pre-dose at visit 2, 9 and 16.

Assessment of binding antibodies against concizumab (anti-drug antibodies (ADA)) will be performed at specialised laboratories whereas assessment of neutralising antibodies will be performed at Novo Nordisk A/S.

Analysis for ADA will be done as listed in [Table 2–1](#), with a bridging ECL assay (binding ADA assay), using labelled concizumab for antibody capture and detection. If a sample is confirmed positive in the confirmatory assay, the sample is considered antibody positive. Confirmed positive samples will be characterised for binding to IgG backbone, CDR region or the S241P mutation.

Protocol
Trial ID:NN7415-4255
UTN:U1111-1179-3872
EudraCT no.:2016-000614-29

~~CONFIDENTIAL~~

Date: 28 August 2018
Version: 5.0
Status: Final
Page: 68 of 127

Novo Nordisk

Furthermore, positive samples will be characterised for neutralising activity using a modified TFPI functionality assay (neutralising ADA assay). All antibody assays are validated according to international guidelines and recommendations.

The following analyses will be available:

- Anti-concizumab antibody assay
- Specificity assay (Anti-concizumab antibodies cross reacting with IgG4 backbone, CDR region or S241P mutation)
- Anti-concizumab neutralising antibody assay

Samples will be drawn at all visits except at visit 3. The binding ADA samples will be analysed in batches during the trial and results will be available to the data monitoring committee approximately every third month after the first patient has been dosed (Section [12](#)). Neutralising antibodies will be analysed and reported at the end of trial. A detailed description of the assay methods will be included in the antibody analysis report at the end of the trial.

Investigators will be notified in case their patient is shown to have developed binding and/or neutralising antibodies against concizumab.

Samples for the determination of anti-drug antibodies collected during the treatment period must be drawn prior to administering trial products.

In the event that a trial patient develops binding ADAs towards concizumab during the course of the trial and has measurable binding ADAs at his End of Trial visit, the patient may attend an ADA follow-up visit. The ADA positive patients will be called for additional visits, e.g. every 4 to 6 weeks, for safety assessment and blood sampling for binding ADA and PD markers (free TFPI and Thrombin generation). The ADA positive patients will be followed no longer than one year after End of Trial.

Hypersensitivity

If suspicion of a hypersensitivity reaction occurs, patients should be instructed to contact the site staff as soon as possible for further guidance, see Section [12.1.5](#).

In the event of a severe local and/or systemic hypersensitivity reaction possibly or probably related to trial product, blood sampling for assessment of anti-concizumab IgE antibodies as well as anti-concizumab antibodies should be conducted in relation to the reaction and no later than 1-2 weeks after the event. Additional testing may be performed if deemed relevant (e.g. anti-Host Cell Proteins (HCP) antibodies).

In the event of a severe systemic hypersensitivity reaction to trial product it is recommended also to test for tryptase (total and/or mature tryptase) within 3 hours of the reaction. Moreover, a baseline

Protocol
 Trial ID:NN7415-4255
 UTN:U1111-1179-3872
 EudraCT no.:2016-000614-29

~~CONFIDENTIAL~~

Date: 28 August 2018
 Version: 5.0
 Status: Final
 Page: 69 of 127

Novo Nordisk

tryptase measurement is necessary 1-2 weeks after the immediate severe hypersensitivity reaction due to individual to individual variation in tryptase baseline concentration.

A follow up visit should be conducted 3-4 weeks post the allergic reaction with repeated blood sampling for assessment of anti-concizumab IgE antibodies as well as anti-concizumab antibodies and if possible also at a visit 3 months post the hypersensitivity reaction for assessing the persistence of the IgE response. Tryptase measurements are not required at the follow up visits.

Additionally, basophil activation testing may be performed if deemed relevant. This can be performed using existing samples and/or by analysing the patient's basophil cells from an additional blood sample taken 3-4 weeks and no later than 2 months after the event. Similarly, prick tests and/or intra-dermal tests may be performed if relevant using trial product or components of trial product. Complement may be measured in case of suspicion of immune complex mediated hypersensitivity reactions.

Results from the following additional tests will be reported to Novo Nordisk Safety Operations for inclusion in the ARGUS database and included in the narratives, if measured:

Test to be performed in case of severe hypersensitivity

- Anti-concizumab IgE antibodies
- Anti-concizumab antibodies (additional to scheduled time points)

Additional testing may be performed if deemed relevant e.g

- Anti-Host Cell Proteins (HCP) antibodies
- Anti-HCP IgE antibodies
- Basophil activation results
- Prick test/intra-dermal test
- Complement test results

Furthermore, it is recommended locally to test for

- Tryptase (total and/or mature tryptase)

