Turoctocog alfa (rFVIII) 2000 IU/vial and isotonic sodium chloride (solvent). Turoctocog alfa (rFVIII) is for intravenous administration.

Table 2-2 Flow chart explanatory descriptions

Footer	Description
a	Concizumab administration is performed at home except for visit 2 where concizumab administration will take place at the trial site.
b	The duration of the visits will last according to patient's individual training need on concizumab administration, NovoPen [®] 4, eDiary training etc. Visit 3 will be a phone call to the patient.
c	For patients being dose escalated a phone call is recommended 1 week after first new dose of concizumab.
d	Daily dosing preferably at the same time in the morning.
e	Evaluation of laboratory results obtained from samples taken at screening.
f	Bleeding episodes occurring between visit 1 and visit 2 or at site should be registered in the eCRF. All bleeding episodes except for severe occurring after visit 2 at home should be registered in the eDiary. Severe bleeding episodes must be registered in the eCRF.
g	Turoctocog alfa will be given to treat breakthrough bleeding episodes either in the clinic or at home.
h	At visit 9 and 16 all blood samples should be collected pre-dose. Patients must not treat themselves with concizumab until sampling has been performed. For unscheduled PK-session visit all blood samples should be collected pre-dose except for post dose samples
i	Only body weight should be measured.
j	Vital signs should be evaluated before and after trial drug administration at visit 2.
k	Sampling for FVIII activity at screening should be postponed if the patient has received FVIII within 96 hours and medical records documenting the severity of haemophilia are not available.
l	FVIII activity and FVIII inhibitor tests should only be collected if reduced effect of turoctocog alfa or FVIII inhibitor development is suspected.
m	In case of clinical signs of e.g. hypersensitivity reactions or immune related events are seen, additional samples for ADAs may be taken. All antibody samples from the affected patient will be analysed on an ongoing basis. If antibodies are detected additional samples will be taken and stored for characterisation of the antibodies.
n	Only dispensing of turoctocog alfa and sodium chloride.

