5.3.1 Dose escalation

Bleeding episodes will be assessed during the trial both at scheduled visits and also between visits. The first 2 weeks of the treatment with concizumab 0.15 mg/kg is considered as a run-in period. Hence the bleeding episodes occurring during the first 2 weeks should not influence a dose escalation decision.

All spontaneous bleeding episodes (sBEs) are counted from 2 weeks after visit 2 (first-dose visit) until visit 16 (end-of-treatment visit), i.e. a total of up to 124 weeks. Dose-escalation will be based on the number of spontaneous, treated bleeding episodes in patients within preceding 12 weeks. However, before dose-escalation can occur, to ensure the safety of the patients, the investigator must take into account the full clinical picture the patient is presenting with and all available laboratory results, including coagulation parameters.

Dose 0.15 mg/kg:

When a sBE occurs, the investigator will determine if ≥ 3 sBEs have occurred within the preceding 12 weeks since visit 2+2weeks (including the current sBE). If yes, and if investigator deems it safe, the patient will have to be dose escalated from 0.15 to 0.20 mg/kg at the next scheduled visit. If the investigator judges that this visit is scheduled too late, he/she should contact the patient for an unscheduled visit.

Dose 0.20 mg/kg:

When an sBE occurs, the investigator will determine if ≥ 3 sBEs have occurred within the preceding 12 weeks (including the current sBE), counting only new sBEs from the beginning of the 0.20 mg/kg treatment period. If yes, and if investigator deems it safe, the patient will have to be dose escalated from 0.20 to 0.25 mg/kg at the next scheduled visit. If the investigator judges that this visit is scheduled too late, he/she should contact the patient for an unscheduled visit.

Dose 0.25 mg/kg:

Patients are not dose escalated further regardless of the number of sBEs. When an sBE occurs, the investigator will determine if ≥ 3 sBEs have occurred within the preceding 12 weeks (including the current sBE), counting only the new sBEs from the beginning of the 0,25mg/kg treatment period. If yes, then the patient must be discontinued from treatment due to lack of efficacy, see Section [6.4](#).

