6.4 Criteria for premature discontinuation of trial product

The patient may be prematurely discontinued from trial product at the discretion of the investigator due to a safety concern.

The patient must be prematurely discontinued from trial product if the following applies:

1. Included in the trial in violation of the inclusion and/or exclusion criteria
2. Simultaneous participation in another clinical trial of an approved or non-approved investigational medicinal product.
3. Incapacity or unwillingness to follow the trial procedures
4. Anaphylactic reaction
5. Thromboembolic event
6. Event of disseminated intravascular coagulation (DIC)
7. Development of inhibitors to Factor VIII (≥ 0.6 BU)
8. Lack of efficacy due to neutralising antibodies towards concizumab
9. Lack of efficacy defined as ≥ 3 treated sBEs within the previous 12 weeks in patients being treated with the highest dose level (0.25 mg/kg) of concizumab.

See Section [8.1.4](#) for procedures to be performed for patients discontinuing trial product prematurely.

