6.7 Rationale for trial population

The most important reason for choosing the trial population, haemophilia A without inhibitors, is that there is a significant unmet medical need in this patient population for a treatment option which reduces the burden associated with the current care, including small volume s.c. administration instead of i.v. Finally, the trial population reflects the patient population that will be selected in a potential subsequent phase 3 trial in which the efficacy and safety of concizumab is to be confirmed.

Protocol
 Trial ID:NN7415-4255
 UTN:U1111-1179-3872
 EudraCT no.:2016-000614-29

~~CONFIDENTIAL~~

Date:	28 August 2018	Novo Nordisk
Version:	5.0	
Status:	Final	
Page:	40 of 127	

7 Milestones

Planned duration of recruitment period first patient first visit – last patient first visit (FPFV-LPFV):
 4 months

FPFV: 16-Aug-2017
 FPFT: 30-Aug-2017
 LPFV: 16-Dec-2017
 Planned LPLV: 31-Mar-2020

The total duration of concizumab treatment in the trial is at least 76 weeks for an individual patient enrolled in the trial for concizumab treatment at visit 2.

End of trial is defined as last patient last visit (LPLV).

Recruitment:

The screening and enrolment rate will be followed closely via the interactive web response system (IWRS) in order to estimate when to stop screening. All investigators will be notified immediately when the recruitment period ends, after which no further patients may be screened and the IWRS will be closed for further screening. All patients screened during the recruitment period and found eligible for enrolment can be enrolled within the timelines specified in the flow chart (see Section [2](#)).

Trial registration:

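### Stopping is mandatory for lack of efficacy due to neutralising antibodies, but the only neutralising assay is scheduled for the end of trial, too late to inform that stop

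*Protocol*

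**What the plan says.** Section 6.4 lists the conditions under which trial product must be stopped. Item 8 is "Lack of efficacy due to neutralising antibodies towards concizumab". Item 9 is three or more treated spontaneous bleeds within 12 weeks at 0.25 mg/kg, and it needs no antibody result.

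Section 8.5.2.7 takes antibody samples at every visit except visit 3 and handles them in two streams. For the first, "The binding ADA samples will be analysed in batches during the trial", with results going to the data monitoring committee about every third month. For the second, confirmed positives are tested for neutralising activity in a modified TFPI functionality assay, but "Neutralising antibodies will be analysed and reported at the end of trial". Investigators are to be told of binding and neutralising positives, with no timing given. Section 7 equates the end of trial with LPLV and gives "Planned LPLV: 31-Mar-2020".

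Section 5.3.1 covers loss of efficacy below the top dose. At 0.15 mg/kg, with three or more spontaneous bleeds in 12 weeks and if the investigator considers it safe, "the patient will have to be dose escalated from 0.15 to 0.20 mg/kg at the next scheduled visit". The same rule moves a patient from 0.20 to 0.25 mg/kg.

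Note m in Table 2-2 reads "In case of clinical signs of e.g. hypersensitivity reactions or immune related events are seen, additional samples for ADAs may be taken", and continues "All antibody samples from the affected patient will be analysed on an ongoing basis". Section 8.5.3 states without qualification that antibody measurements are analysed after LPLV.

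**The concern.** Item 8 asks the investigator to attribute a loss of efficacy to one cause, and the only assay that tests for that cause is scheduled to report when dosing is over. Until then the default at the two lower doses is to give more drug, whereas item 8, if it applied, would require stopping. At stake is whether a mandatory stopping rule can be applied on direct evidence. The sponsor regards the mechanism as possible: section 18.1 says antibodies might inhibit the drug's function, and the rationale for amendment 3 says binding antibodies can affect PK and so efficacy and safety. That amendment extended investigator notification to binding antibodies but left the neutralising assay where it was.

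**Working it through.** No stated statistical figure is involved. The check compares dates and sets the relevant sections side by side.

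**1. When the scheduled neutralising result arrives.** Section 8.1.10.3 puts visit 16 on the last day of treatment, and no patient's visit falls after LPLV. A result issued at LPLV therefore comes at or after the last dose in this trial for everyone. The section 7 dates agree:
- First patient dosed 30 Aug 2017: to 31 Mar 2020 is 944 days, and 944 / 7 = 134.9 weeks. Treatment lasts at most 126 weeks, so the result comes at least 134.9 − 126 = 8.9 weeks after the last dose.
- Last patient screened 16 Dec 2017 and dosed 14 to 21 days later, that is 30 Dec 2017 to 6 Jan 2018: to 31 Mar 2020 is 822 to 815 days, or 117.4 to 116.4 weeks. This patient can be dosed up to LPLV, but not beyond it.

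**2. What is available earlier.**

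| Source | In-trial result? | Neutralising result? | Lack of efficacy named as trigger? |
|---|---|---|---|
| Binding antibodies (8.5.2.7) | Yes, in batches | No | No |
| Free TFPI (8.5.1.2) | Sampled at assessment visits | No | No |
| Concizumab level (8.5.2.8) | Sampled at all visits except 1 and 3 | No | No |
| Note m | Possible; trigger is open-ended | Not promised; on detection, further samples are stored for characterisation | No; hypersensitivity and immune events are the examples |
| Extra central sampling (8.5) | Possible | No; the antibodies named are IgE and binding | No; adverse event follow-up is the example |

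If binding results reach investigators at the interval given for the committee (an assumption, about 13 weeks), visits every 4 weeks in the main part give 13 / 4 = 3.3 visits per batch, and visits every 8 weeks in the extension give 13 / 8 = 1.6. An escalation at the next scheduled visit could then precede even the binding result.

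**3. Who can be affected.** The patient must be binding-positive, since the neutralising assay is run only on confirmed positives, and must be losing efficacy.
- At 0.15 or 0.20 mg/kg, 5.3.1 directs escalation if judged safe, whereas item 8 would require stopping if neutralising antibodies are the cause.
- At 0.25 mg/kg, item 9 stops the patient in any case.

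**4. What is not affected.** The timing of the neutralising assay does not enter the sample size in 17.1 or the bleeding-rate model in 17.3. The antibody summary in 17.6.2 concerns binding antibodies only.

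**5. A separate inconsistency.** Section 8.5.3 puts antibody analysis after LPLV. Section 8.5.2.7 analyses binding antibodies during the trial and notifies investigators. Both cannot be right. Section 8.5 says only that such analysis is often after LPLV, which is compatible with 8.5.2.7.

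**The case against.** The strongest reply is that item 8 names a cause and demands no particular assay. The neutralising test is presented in 8.5.2.7 as characterisation of positive samples, and nothing ties it to item 8. An investigator told of a binding-positive patient can look at free TFPI, which bears on whether the drug still engages its target, and at the concizumab level. Section 5.3.1 already requires the laboratory results at hand to be weighed before escalating. Note m is worded by example, so an earlier run is not excluded, and amendment 3 deliberately brought binding results forward with efficacy in mind.

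Most of this stands. A reader might infer that item 8 cannot be applied at all, or that the end-of-trial assay is its designated test; the documents support neither. What remains is that binding is not the same as neutralising, which is why the protocol has a second assay. The other markers may show that drug effect is falling but do not by themselves show that neutralising antibodies are the reason. No text requires, or even names, a neutralising test when efficacy is lost.

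**Conclusion.** The mismatch is real and in the current text: followed as written, the schedule cannot put a neutralising result before an investigator while that patient is being dosed in this trial. It weakens the evidence for one mandatory stop in few patients, possibly none; section 18.1 reports no antibodies in clinical trials so far. It is worth correcting because the correction is cheap, not because the trial's conclusions are at risk.

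Three larger readings should be resisted. The months between a 76-week patient's last dose and LPLV do not measure harm, because item 8 has nothing left to stop once dosing has ended. The bleeds needed to climb to 0.25 mg/kg and meet item 9 are the path for any non-responder and are not caused by assay timing. The absence of antibodies in the earlier trials does not let one estimate how many patients here would be both neutralising-positive and losing efficacy.

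The conclusion assumes the planned dates in section 7, and that no document outside the protocol, such as a laboratory manual, provides for an earlier neutralising run. The inconsistency in 8.5.3 holds regardless.

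**What to change.** - **Section 8.5.2.7:** run the neutralising assay during the trial on confirmed binding-positive samples when the patient meets the lack-of-efficacy or escalation criterion, and report the result to the investigator, before escalation where possible. Other samples can stay on the end-of-trial schedule.
- **Table 2-2, note m:** add lack of efficacy to the triggers, so that the patient's antibody samples are analysed at that point without waiting for the next batch.
- **Section 8.5.3:** reword the sentence placing antibody analysis after LPLV so that it matches the in-trial binding batches and investigator notification in 8.5.2.7. The wording in 8.5 can stay.

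Whether item 8 applies to a given patient remains a clinical decision. The cost is a short amendment and a few unbatched runs of an assay already planned at the sponsor's laboratory, on what may be very few samples or none.
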